9.4.1.3 France

The French National Health Data System (Système National des Données de Santé (104) is the largest and most comprehensive healthcare dataset available in Europe. It covers 99% of the French population, approximately 66 million patients (9). Individuals enter SNDS at birth or by immigration and exit at death or emigration.

SNDS includes anonymised administrative and healthcare claims data from the French national health care insurance system databases. The SNDS is composed of:

- the French National Health Insurance database (*Système national d'information interrégimes de l'assurance maladie* [SNIIRAM]) available since 2008;
- the French hospital discharge summaries (*Programme de médicalisation des systèmes d'information* [PMSI]) available since 2006;
- the national death registry (*Centre d'épidémiologie sur les causes médicales de Décès* [CépiDC]).

These databases can be linked by a unique patient identifier (104).

Since 2008, SNIIRAM includes the outpatient reimbursed health expenditures (*données de consommation interrégimes* [DCIR]) which allows studying consumption of care. Data from DCIR (outpatient care) and PMSI (inpatient care) can be linked for follow-up across different settings of care including outpatient practice and hospital admissions related to administration of medications, surgery, and obstetrics.

Reimbursed drugs dispensed through retail pharmacies are available through DCIR and drugs are identified by their ATC code. The date of dispensing, quantity, and brand name are also available. Information on route of administration is available and dose may be estimated from DDD. Information on drug indication is only possible for the inpatient setting, derived from diagnoses.

Hospital administered treatments are available through PMSI, if they are part of the list of high-cost drugs (*medicaments listés en sus*). Inclusion in the list allows the reimbursement of drugs, in addition to the hospital episode reimbursement.

Through the PMSI, SNDS includes medical summaries of all hospitalisations from private or public hospitals, including date of stay, medical procedures, devices implanted during the hospital stay, primary diagnosis (main reason for admission) and related diagnosis. These data are encoded according to the ICD-10.

SNDS contains data on the presence and diagnosis date of long-term chronic disease (LTD). LTD is used together with PMSI to identify patients, namely those with SLE. Patients with LTD are eligible for 100% reimbursement of healthcare expenditure. The request for attribution of LTD is made by the general practitioner and it is not mandatory. Thus, it may be missing, for instance, if the medical expenses are already covered by another chronic disease or the treatment is not expensive. Diagnoses are coded using ICD-10.

SNDS also includes demographic data (including age, sex, place of residence, complementary universal health coverage status (as proxy to socio-economic status), date of death), health encounters, dispensations, medical devices, and laboratory tests (without results) (9). Information on occupational diseases and sick leaves are also available (104).

Data from DCIR and PMSI are annually updated and can be linked for each patient. At the time of the feasibility assessment, data were available until the end of 2021.

Study-specific data availability

The estimated annual number of pregnancies in women with SLE eligible for the MCM analysis and the select pregnancy loss outcomes analysis is 178 and 223, respectively (see Section 9.5.1 and Table 9).

Mother-offspring linkage is available since 2012, and all live births and stillbirths can be linked (10). This linkage is achieved using a deterministic approach.

In France, anifrolumab received marketing authorisation in February 2022 and entered the market in April 2022 (Table 4).

In France, reimbursed drugs dispensed through retail pharmacies are available. Data on SLE SOC drugs are available, except for voclosporin and mepacrine, which are not marketed in France. Some drugs, such as methotrexate, mycophenolate mofetil, cyclophosphamide, and cyclosporine are available if the oral forms are used. Chloroquine use is available until the end of September 2022, when the last product was withdrawn from the market. Data on biologics is available from 2008 for outpatient (DCIR) and inpatient (PMSI) settings. For hospital administered drugs, only expensive drugs are captured in SNDS. Rituximab and immunoglobulin G – administered as IV in the hospital sector – are available as they are part of the list of high-cost drugs. Exposure to anifrolumab can only be captured provided it is among the high-cost drug list. Anifrolumab was on the high-cost drug list from 28 June 2021 to 12 May 2022 and was thus captured during that period. Health authority assessment procedures to determine reimbursement approach for anifrolumab is currently ongoing. The suitability of France as a data source, will be re-evaluated when a decision on reimbursement has been made, as this will influence the ability of SNDS to capture the exposure of interest.

In France, all study outcomes of interest are available or partially available ([Table 16](#)), as well as maternal characteristics, other baseline characteristics and covariates ([Table 17](#)).

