A group of pregnant women comparable to the exposed, with moderate/severe SLE, will be selected as the comparator group. Moderate and severe SLE patients when compared to non-SLE population are at increased risk of adverse outcomes, because of SLE disease activity and the effect of SLE-related medication use. Therefore, the choice of this internal comparison group has been made to minimise confounding by SLE disease severity/activity and medications.

Descriptive analyses of the population under study, the risk in the exposed and unexposed cohorts, and the relative risk of the primary and secondary outcomes of the study will be provided for pregnancies/offspring of women with moderate/severe SLE exposed to anifrolumab anytime during pregnancy (for MCM during the first trimester) compared with a comparator group of

women with moderate/severe SLE exposed to SLE SOC and unexposed to anifrolumab anytime during pregnancy (for MCM during the first trimester).

Aggregated country-specific results for the primary objectives will be combined (if feasible) via a meta-analytic approach, providing a pooled estimate across all data sources.

Population

Study time period

The start of the study period will be the market launch date of anifrolumab in each country, as follows: 11 March 2022 for Denmark, market launch date to be confirmed for Finland, 19 April 2022 for France, 11 March 2022 for Germany, 23 August 2021 for the USA. The end of study period, defined as the last possible day of follow-up when all patients still active are censored, is likely to differ between countries. It will depend on the length of data lag in each country at the time of last data extraction (31 March 2031).

Participants

To address the research questions eligible cohorts will be identified through a nested selection process. An *overall source population* will be created for data extraction (*STEP 1*) and split into *exposed to anifrolumab source population* and *unexposed to anifrolumab source population* (*STEP 2*).

Then criteria common to exposed and unexposed to anifrolumab source populations will be applied to create post-data extraction *exposed to anifrolumab study population* and *unexposed to anifrolumab study population* (*STEP 3*) from which the cohorts of analyses will be derived (*STEP 4*).

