Exposure to SLE SOC and/or co-medication (excluding biologics) will be assessed from LMP2 until end of first trimester for the outcome of MCM, and from LMP2 until end of pregnancy for all other outcomes. A look back period of 5-half-lives of relevant drugs will be considered. This is to account for prescription/dispensations/administrations prior to LMP2 that gave rise to *in utero* exposure of the offspring.

SLE SOC and/or co-medications are assumed to be continued throughout pregnancy. It is common for SLE to be more active during pregnancy with a high prevalence of flares (11, 12, 28, 63, 67). The risk of adverse outcomes among pregnant women who have SLE is related to disease severity (e.g., involvement of the kidneys) and activity during pregnancy (29, 39), thus it is expected that SLE treatment would occur even in pregnancy. A sensitivity analysis accounting for actual use of SLE SOC during pregnancy is presented in Section 9.7.5.

Exposure to anifrolumab will be assessed from LMP2 until end of the first trimester for the outcome of MCM, and from LMP2 until end of pregnancy for all other outcomes (see Section 8.1), or until censoring, regardless of duration of exposure. Considering anifrolumab window of clearance (16 weeks, see definition above), all patients who receive prescriptions/dispensations/administrations of anifrolumab in the 16 weeks prior to LMP2 or during pregnancy will be considered exposed (2).

Offspring whose mother had no anifrolumab prescription/dispensations/administration in the 16 weeks prior to LMP2 or during the first trimester for the outcome of MCM, or during pregnancy for all other outcomes, will be considered unexposed.

Although, the foetus is most at risk during the period of organogenesis (i.e., during the first trimester of pregnancy), exposures during other gestational time periods may also be associated with adverse outcomes (e.g., spontaneous abortion, stillbirth, or other pregnancy complications). The identification of critical windows of exposure *in utero* provides clues to possible mechanisms of the pregnancy loss and provides guidelines for protection of the foetus. An exploratory analysis focusing on the effect of *in utero* exposure to anifrolumab in different trimesters of pregnancy on the

¹⁰ The respective half-lives of SLE SOC and co-medications will be provided in the SAP.

occurrence of select pregnancy loss outcomes (composite of spontaneous abortion and stillbirth will be assessed:

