The summary of the estimated annual number of pregnancies in women with moderate-to-severe SLE eligible for the primary outcome analysis are shown in [Table 9](#) for each data source and anifrolumab exposure proportion scenarios. The MCM analysis will only consider the pregnancies where anifrolumab exposure occurs during the first trimester of pregnancy, and it is assumed that 80% of all anifrolumab exposed pregnancies have exposure to anifrolumab within the first trimester of pregnancy. Based on these estimates and assuming that 5% of pregnancies in moderate to severe SLE patients are exposed to anifrolumab, the total number of anifrolumab exposed patients by the end of the study time period (September 2030 in USA, September 2028 in other study countries) is estimated to be 249 (82 [Carelon Research], 81 [DAPI], 5 [Denmark], 3 [Finland], 73 [France] and 5 [RHEKISS]) patients ([Table 10](#)) for the select pregnancy loss outcome

and 175 (51 [Carelon Research], 56 [DAPI], 4 [Denmark], 3 [Finland], 58 [France] and 3 [RHEKISS]) for the MCM outcome.

Under the assumption of 10% of pregnancies in moderate to severe SLE patients exposed to anifrolumab, the estimated number at the end of the study period is 497 (163 [Carelon Research], 162 [DAPI], 11 [Denmark], 7 [Finland], 145 [France] and 9 [RHEKISS] patients (Table 11) for the select pregnancy loss outcome and 353 (102 [Carelon Research], 114 [DAPI], 8 [Denmark], 6 [Finland], 116 [France] and 7 [RHEKISS]) for the MCM outcome.

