To identify the data sources that are likely to contribute to the meta-analysis, the probability of observing at least one MCM or select pregnancy loss outcomes event in the data source during the study period was estimated. Data sources that have a $\geq 90\%$ probability of observing at least one outcome event will be considered for inclusion in the meta-analysis level study size and power calculations (cells highlighted in Table 10 and Table 11). Under the assumption of a 5% anifrolumab exposure, the data sources of Carelon Research (USA), DAPI (USA) and France each have $>90\%$ probability of observing at least one event for each primary outcome (MCM or select pregnancy loss outcomes) in the exposed group during the study time period. Under the assumption of 10% anifrolumab exposure, the data sources of Carelon Research, DAPI, Denmark and France each have $>90\%$ probability of observing at least one select pregnancy loss outcome event in the exposed group during the study time period, and the data sources of Carelon Research (USA), DAPI (USA) and France each have $>90\%$ probability of observing at least one MCM outcome event in the exposed group during the study time period (Table 11).

Assuming a two-year extension of the study period (study final report in 2034) and under the assumption of 5% anifrolumab exposure, the data sources of Carelon Research (USA), DAPI (USA) and France would each have $>90\%$ probability of observing at least one select pregnancy loss outcome or MCM event. Under an assumption of 10% anifrolumab exposure, the data sources of Carelon Research (USA), DAPI (USA), Denmark, France and RHEKISS would each have $>90\%$ probability of observing at least one event for the select pregnancy loss outcomes; and Carelon Research (USA), DAPI (USA) and France data sources would each have $>90\%$ probability of observing at least one event for the MCM outcome.

As the exact proportion of exposure to anifrolumab among pregnant SLE women is unknown at this time, these assumptions will be evaluated in the first interim report, and the study milestones will be adjusted as necessary to ensure a sufficient sample is obtained to address the research objectives.

Table 9: Estimated annual number of pregnancies in women with SLE eligible for the primary outcome analysis by the data sources and with 5% and 10% of exposure to anifrolumab among pregnant SLE women.

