- Considering the IV infusion as the current route of administration of anifrolumab, definition of exposure may be challenging. Outpatient visits with a recording of the relevant ATC and/or procedure codes, rather than the prescribing/dispensing records may be needed to determine the exposure status of study subjects. This could potentially lead to misclassification of the exposure (i.e., use of anifrolumab may be under-detected). Such a potential bias would move the measure of association towards the null, since the exposure status of the cohorts would not be fully established, and the cohorts of exposed and non-exposed pregnancies will therefore be more similar. The feasibility assessment was used to inform the selection of data sources to minimise the impact of this potential limitation.
- It is assumed that all prescribed drugs are filled and then taken by patients in a compliant manner. Non-compliance would result in misclassification of exposure and could cause an underestimation of the association between exposure and outcome.
- SLE severity and activity algorithms were adapted from a previously published algorithm used in other settings (50), including the data sources included in this study, to meet current criteria and recommendations of medication use in SLE patients. The assumptions made for the proposed adaptations were based on the experience of the study team, including database analysis expertise and clinical knowledge, but also on literature relevant to the subject, ensuring that sound assumptions are made.
- For some of the diagnoses included in the activity algorithm, distinguishing clinical manifestations (i.e., acute illnesses) that define active SLE from comorbidities may not be possible (e.g., renal impairment). Therefore, there is a possibility of misclassifying signs of active disease as a comorbidity. The impact of this misclassification is considered minimal as adjustments will be made for disease activity as well as disease severity.
- Since anifrolumab prescribing is not recommended in pregnancy, uptake of the drug in pregnancy may be extremely limited at least in the initial years of launch post-authorisation, thus hampering the feasibility of the safety analyses with respect to study size targets.

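### French enrolment opens on 19 April 2022, but the only reported period of anifrolumab capture in SNDS ended 23 days later, and the protocol has no rule for the uncaptured interval and no power figure without France

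*Protocol*

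**What the plan says.** Section 9.4.1.3 makes French exposure data depend on one administrative condition: "Exposure to anifrolumab can only be captured provided it is among the high-cost drug list". It reports one listing period: "Anifrolumab was on the high-cost drug list from 28 June 2021 to 12 May 2022 and was thus captured during that period". Reimbursement was still under assessment at the time of writing, and the section adds: "The suitability of France as a data source, will be re-evaluated when a decision on reimbursement has been made". Table 8 marks French anifrolumab capture as partial, on the same condition.

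The start of the French study period in the Abstract is "19 April 2022 for France". Table 4 repeats that date for the start of enrolment and ends enrolment on 29 September 2028.

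Section 9.3.1 defines the unexposed group by absence of a record: "Offspring whose mother had no anifrolumab prescription/dispensations/administration in the 16 weeks prior to LMP2", or during the outcome-specific window, counts as unexposed. Step 2B in Section 9.2.2 admits such a pregnancy to the comparator if SLE SOC is recorded.

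Section 9.5.1.2 counts France in full. At 10% uptake the exposed total is "353 (102 [Carelon Research], 114 [DAPI], 8 [Denmark], 6 [Finland], 116 [France] and 7 [RHEKISS]) for the MCM outcome". At 5% uptake it states that "the data sources of Carelon Research (USA), DAPI (USA) and France each have" more than 90% probability of at least one event for each primary outcome. Table 13 includes France in every scenario.

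**The concern.** Anifrolumab is an add-on to SOC. A French user treated while the drug is off the list leaves no anifrolumab record but does leave SOC records, so the protocol's rules place her in the comparator. Even a pregnancy with LMP2 on the first enrolment day has only 23 days of reported capture ahead of it. A pregnancy conceived soon after any re-listing has a 16-week look-back that reaches into the gap.

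Two different harms follow, depending on what happens next. If the drug is re-listed and France is kept, treated pregnancies dilute the French comparator and move the RR towards 1. In a study meant to rule out an RR of 2.5, that is the unsafe direction. If the drug is not re-listed, France yields almost no observable exposed pregnancies, and the planned sample is smaller than Section 9.5 states. The protocol has neither a rule for the first case nor a power figure for the second.

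**Working it through.** **Capture window.** 19 April to 12 May 2022 is 23 days (24 counted inclusively). From launch to the end of the French study period, 30 September 2028, is 6.45 years.

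**What Section 9.5 assumes for France.** Annual eligible French pregnancies are 178 for MCM and 223 for pregnancy loss (Section 9.4.1.3, Table 9).
- MCM: 178 × 10% × 6.45 = 115, stated 116.
- Pregnancy loss: 223 × 10% × 6.45 = 144, stated 145.

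The stated counts therefore assume unbroken capture from launch.

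**French share of the MCM meta-analysis.** 102 + 114 + 116 = 332, and 116/332 = 34.9%. Table 12 prints 34% (71 of 210). Against all six sources the share is 116/353 = 32.9%.

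**Power.** I followed Section 9.5.1.3: binomial events at 7% in both groups, true RR 1, source-level log RR with Poisson standard error √(1/a + 1/b) for a exposed and b comparator events, inverse-variance fixed-effect pooling, and power as the share of 95% upper bounds below 2.5. The table uses the model-based standard error, with 400,000 runs per cell.

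| MCM scenario | Stated, with France (1:2 / 1:3) | Reproduced, with France | Without France |
|---|---|---|---|
| 10% uptake, 2032 | 96% / 98% | 96% / 98% (n = 332) | 84% / 90% (n = 102 + 114 = 216) |
| 5% uptake, 2032 | 69% / 72% | 66% / 73% (n = 165) | 46% / 52% (n = 51 + 56 = 107) |
| 5% uptake, 2034 | 80% / 84% | 79% / 85% (n = 206) | 58% / 65% (n = 62 + 69 = 131) |

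The one visible mismatch, 66% against 69%, disappears with a robust standard error (69%). On that basis the figures without France at 5% uptake are 49%/55% (2032) and 61%/68% (2034). Pregnancy-loss power without France stays above 99% even at 5% uptake (82 + 81 exposed).

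**Bias if France is kept after re-listing.** If a fraction c of the comparator is in fact exposed and the true RR is 2.5, the observed RR is 2.5 / (1 − c + 2.5c) = 2.5 / (1 + 1.5c).
- Worst case, a comparator drawn wholly from the gap with every user missed: c = 0.05 gives 2.33 and c = 0.10 gives 2.17.
- Assumed two-year gap in 6.45 years, no adjustment for calendar year: c = 0.05 × 2/6.45 = 0.016 gives 2.44, and c = 0.10 × 2/6.45 = 0.031 gives 2.39.
- Taking a French weight of about 35% and no bias elsewhere, the pooled RR in the two-year case is exp(0.35 ln 2.44 + 0.65 ln 2.5) = 2.48, and 2.46 with 2.39 in place of 2.44.

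**The case against.** The strongest reply is that the protocol already treats France as provisional. The re-evaluation sentence directly follows the listing dates, and Table 8 repeats the condition. If France is dropped, nobody is misclassified. If the drug is never re-listed, Section 9.7.1 requires an event in each exposure group before an RR is estimated, so France would probably contribute none. This stands, and it makes the bias conditional on re-listing and retention. It does not remove the defect, because the re-evaluation decides only whether France stays and leaves the start date and the gap untouched.

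Second, year of conception is a listed confounder for every outcome in Table 7. If it is modelled flexibly, pregnancies from years with no captured exposure would get propensity scores near zero, and would rarely be matched or carry weight. This would shrink the bias in the adjusted RR. But Section 9.7.1 only says that Table 7 variables will be considered, and pregnancies straddling the boundary would remain.

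Third, Section 9.9 already discloses the general risk for infused anifrolumab: "This could potentially lead to misclassification of the exposure (i.e., use of anifrolumab may be under-detected", with bias towards the null. It is not tied to the French gap and prescribes no handling of it.

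Fourth, Sections 9.4 and 9.5.1.2 provide for additional data sources, a longer study and an interim review of assumptions. These could mitigate lost sample. However, at 5% uptake the two-year extension no longer reaches 80% power without France.

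**Conclusion.** The inconsistency is real: enrolment dates and exposed counts assume capture from launch, while the reported listing ended 23 days later. It should be fixed, but it does not invalidate the design.

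A reader might infer that French users in the gap will certainly be counted as unexposed, or that a true RR of 2.5 would be reported as 2.2. The documents do not support either. Misclassification requires both re-listing and retention of France, and 2.17 needs a comparator drawn wholly from the gap, 10% uptake and every user missed. Under the assumed two-year gap the French RR falls only to 2.44–2.39, and less far if year of conception is balanced.

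A reader might also infer that losing France sinks the MCM objective. At 10% uptake it does not: 216 exposed still exceed the required 210 (1:2) and 183 (1:3), and power is 84%/90%. The loss matters at 5% uptake, where power is already below 80% with France and falls to about 46%/52%. Reducing the count further with an MCM enrolment cut-off for the USA would need a date that Table 4 does not state, so that is left out.

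The power figures rest on the protocol's own 7% prevalence, true RR of 1 and exposed counts.

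**What to change.** In Table 4, replace the French launch date with a rule for both cohorts: enrolment starts when anifrolumab is continuously capturable in SNDS, with LMP2 at least 16 weeks after that date. In Section 9.2.2, exclude any French pregnancy, exposed or unexposed, whose exposure window including the look-back overlaps an uncaptured interval. This also covers any later de-listing. Recompute the French counts in Tables 10 to 12 from the new start date, and add rows without France to Table 13 for both uptake scenarios and both report years.

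The cost is one eligibility rule and one re-run of the existing simulation, before the first extraction planned for 31 May 2025. The price is fewer French comparators from the early years and a less favourable stated power.
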